10.2 Sample Size Considerations

All analyses will be descriptive with no formal hypothesis testing. The sample size was selected based on practical considerations. The primary objective of the study is to assess whether baseline intratumoral CD8+ cell density is correlated with the likelihood of response to talimogene laherparepvec. Analyses for the objective will focus on whether the response rate varies with baseline intratumoral CD8+ cell density. The functional manner in which the response rate may vary with the biomarker is unknown, therefore multiple functional relationships may be examined. It is assumed that 100 subjects (approximately 91% of the enrolled) will have an evaluable baseline intratumoral CD8+ cell density. The adequacy of the sample size was evaluated for one of several possible analyses that evaluates whether the response rate is positively correlated with a high baseline intratumoral CD8+ cell density where a low and high biomarker is defined as a value below versus at or above the sample median, respectively. A one-sided Fisher's Exact test will be performed at a 5% nominal level to explore the hypothesis that the response rate is equal regardless of baseline intratumoral CD8+ cell density. The overall ORR is assumed to be 26.4%. The power for the test will depend on the true response rates in the biomarker subgroups. Assuming the true response rate is 13.2% in the biomarker low subgroup, and 39.6% in the biomarker high subgroup, the power will be 88% to detect a positive association.

A secondary objective of this study is to estimate the objective response rate. Based on the analysis of the OPTiM study, the overall response rate for stage IIIB/C and IVM1c is assumed to be around 26.4% where, among responders, the probability of response onset after 12 months was < 5%. The expected exact 95% CIs for various true ORRs are listed in [Table 4](#). The expected width of the 95% CI is around 18% under these scenarios.

Table 4. Expected 95% Confidence Intervals by Various True ORRs

Subjects enrolled (N)	True	Expected 95% CI (width)
110	20%	13% - 29% (16%)
	30%	22% - 39% (18%)
	40%	31% - 50% (19%)
	50%	40% - 60% (19%)

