10.4.2 Secondary Endpoint (s)

Multiple biomarkers will be examined to assess the correlation between their baseline value and DRR, DOR, and changes in tumor burden as well as the changes in their value during treatment with ORR, DRR, DOR, and changes in tumor burden. The functional manner in which the ORR, DRR, DOR, and change in tumor burden may vary with each biomarker is unknown, therefore multiple functional relationships will be examined to assess overall evidence of an association. Combinations of biomarkers may be explored to assess their predictive value for patient selection. Example analyses include, but are not limited to: (a) the correlation of baseline value as a continuous variable with the odds of OR, DR or the hazard of ending response; (b) a trend test for an increasing ORR, DRR with pre-specified, ordered biomarker categories, (c) a test that the ORR, DRR or hazard of ending response is greater between subgroups of subjects with a high vs. low baseline biomarker value for all possible cut-points for a minimum high biomarker value, (d) a receiver operating characteristic (ROC) analysis (categorical and continuous biomarker values), and (e) calculation of negative predictive value (NPV) and positive predictive value (PPV) for each candidate cut-point for ORR and DRR.

In order to evaluate the correlation between changes in biomarkers during treatment and the effect of treatment on measurable lesions, Pearson's correlation coefficient (r) will be estimated between the biomarker change and the maximum decrease in index lesions, in addition to correlating biomarker changes with ORR/DRR using logistic regression, and duration of response using Cox model regression.

Overall survival (OS), duration of response and time to treatment failure will be summarized by K-M methods. Durable response rate and objective response rate will be presented with 95% CI.

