11.1 General Principles

The main goals of this analysis are: (1) to better understand the distribution of intratumoral CD8+ cell density in the overall population and in subgroups; (2) to explore associations among baseline/change in intratumoral CD8+ cell density and efficacy endpoints; and (3) to explore the clinical potential utility of intratumoral CD8+ cell density cut-off values for patient selection.

Changes in intratumoral CD8+ cell density will be analyzed overall and separately for injected and uninjected lesions.

In principle, mean, standard deviation, median, first and third quartiles, minimum and maximum will be calculated for continuous variables; frequency count and percent will be calculated for binary and categorical variables. P-values will be used mainly as a descriptive measure suggesting comparative strength of association rather than to test hypotheses. Accordingly, nominal p-values will be generated with no adjustment for multiplicity. Analyses will be based on the Safety Analysis Set unless otherwise specified.

CCI

. The

following are some general principles which will be followed to handle such issues for efficacy analyses.

- It is desirable for subgroups to have 10 or more subjects for each dichotomization or categorization scheme, though judgment maybe applied.
- Analyses will be more carefully considered for robustness of results (e.g., K-M curves, model building, comparison between subgroups) when some subgroups have a small number of subjects and/or when there are few events for time-to-event endpoints..

CCI [REDACTED]
[REDACTED]
[REDACTED]
[REDACTED]
[REDACTED].

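### If the all-cut-points CD8+ scan is run, its unadjusted p-values and PPV/NPV need a correction for selecting the cut, and no readable text provides one

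*Protocol*

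**What the plan says.** - Protocol 10.4.2 gives a list of methods opened by "Example analyses include, but are not limited to". Item (c) covers ORR, DRR and loss of response, and looks for a rate or hazard "greater between subgroups of subjects with a high vs. low baseline biomarker value for all possible cut-points for a minimum high biomarker value". Item (e) computes NPV and PPV for each candidate cut-point. The biomarker is generic here.
- SAP 11.1 supplies the link to CD8+. One of its three main goals is "to explore the clinical potential utility of intratumoral CD8+ cell density cut-off values for patient selection".
- SAP 11.1 treats p-values mainly as a descriptive gauge of comparative strength of association, and adds that "nominal p-values will be generated with no adjustment for multiplicity". It prefers subgroups of 10 or more but leaves room for judgment.
- Protocol 10.2 plans one specific test, at the sample median: "A one-sided Fisher's Exact test will be performed at a 5% nominal level to explore the hypothesis". It also says: "The adequacy of the sample size was evaluated for one of several possible analyses". Neither Protocol 10.2 nor 10.4.1 labels it as the lead analysis of the primary endpoint.
- No readable text in either document gives a p-value adjusted for choosing the cut, a resampling step or a validation set. Much of SAP 11.4, including the 11.4.1 to which 11.4.3 refers, is redacted.

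**The concern.** A scan over every cut-point produces many correlated p-values, and attention goes to the smallest. That smallest p-value does not mean what the p-value from a cut fixed in advance means, even as a descriptive measure. Set beside the median-split, trend or continuous-model p-value, it overstates the strength of association because it is the best of many tries. The same applies to PPV and NPV. If they are quoted at a cut chosen because it separated responders from non-responders in these subjects, they are too favourable for new subjects.

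What is at stake is the SAP's cut-off goal. Protocol 7.3 says the sponsor may try to develop a test for likely responders. Protocol 10.3.1 allows the protocol and SAP to be revised if the interim analysis suggests an enhanced effect in a biomarker-defined subgroup. A cut-off that owes much of its apparent separation to selection could feed either step.

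**Working it through.** **Inputs from the documents.** Evaluable subjects: "It is assumed that 100 subjects (approximately 91% of the enrolled) will have an evaluable baseline intratumoral CD8+ cell density". Null response rate: "The overall ORR is assumed to be 26.4" percent. Test: one-sided Fisher's exact at a nominal 5%, stated in Protocol 10.2 for the median split. Preferred minimum subgroup: 10 (SAP 11.1).

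**Assumptions not in the documents.** The same Fisher test is applied at every cut; there are no tied CD8+ values (relaxed in step 5); one biomarker and one endpoint (ORR).

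**Step 1. Reproduce the plan's own figure.** With R responders among 100 and k subjects in the high group, r of whom respond, the one-sided Fisher p is P(X ≥ r), where X is hypergeometric (100, R, k). Enumerating two binomials of 50 with rates 13.2% and 39.6% and summing the probability of tables with p ≤ 0.05 gives power of 88.4%. The protocol states 88%, so the figure reproduces.

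**Step 2. The median split under no association.** Both rates are set to 26.4%. Fisher's test is conservative at this size. With R = 26 and k = 50, 17 versus 9 responders gives P(X ≥ 17) = 0.055 and 18 versus 8 gives P(X ≥ 18) = 0.020, so nothing falls just under 0.05. Averaged over R, P(p ≤ 0.05) = 3.0%.

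**Step 3. The scan under no association.** Responders fall in random order along the CD8+ ranking. The chance that at least one cut has p ≤ 0.05 was found by exact recursion along that ranking, averaged over R ~ Binomial(100, 0.264). A simulation of 40,000 trials agrees to within about 0.2 percentage points.

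| Minimum per subgroup | P(at least one cut with p ≤ 0.05) |
|---|---|
| none | 25.9% |
| 5 | 24.8% |
| 10 | 22.9% |
| 20 | 18.0% |
| 25 | 15.8% |
| median split only | 3.0% |

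At the SAP's preferred minimum, the scan flags a null trial 22.9 / 3.0 = 7.6 times as often as the median split.

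**Step 4. What the best cut looks like under no association (at least 10 per subgroup).** Over all null trials, the cut with the smallest p shows on average about 34% ORR in the high group and 20% in the low group: a gap of 14 points when the truth is zero. PPV is the response rate in the high group and NPV is one minus the rate in the low group. Average PPV at the best cut is therefore 34% against a true 26.4% (7.6 points too high), and average NPV is 80% against a true 73.6% (6.4 points too high). In the null trials where the best cut reaches p ≤ 0.05, the median rates are about 38% and 16%. That is close to the 39.6% and 13.2% the trial was sized to detect.

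**Step 5. Sensitivity.** All with at least 10 per subgroup unless noted.
- One third of values (33 of 100, an assumption) tied at the bottom: 18%. Protocol 2.1 says about one third of melanomas have few or no infiltrating T cells, so ties are plausible.
- Two-sided Fisher: 26.0%. Uncorrected one-sided chi-square: 34.2%.
- DRR at 16% (the OPTiM figure in Protocol 2.2): 19.9%.
- 50 subjects, as at the interim: 14.3%, or 18.6% with no minimum.

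**Step 6. Cost of correcting.** Holding the whole scan to 5% (at least 10 per subgroup) needs a per-cut threshold of about 0.0083. If there is a true step at the median of 13.2% versus 39.6%, the adjusted scan keeps about 83% power by simulation, against 88.4% for the median split alone.

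**The case against.** The strongest reply is that the plan makes no confirmatory claim. Both documents disclaim formal hypothesis testing, and SAP 11.1 calls the p-values descriptive and openly says they are unadjusted. The 5% level belongs to the median split, so applying it to every cut measures a decision rule the plan never states. All of this stands: no error rate is breached. It does not remove the point, because SAP 11.1 gives p-values the job of indicating comparative strength, and the smallest of a scan does that job badly. The optimism in PPV and NPV at a selected cut needs no testing framework at all.

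Three stronger readings are tempting, and the documents support none of them.
- A reader might infer that a cut-off from the scan will be applied to select patients. SAP 11.1 only explores potential utility, and the patient-selection sentence in Protocol 10.4.2 concerns combinations of biomarkers that may be explored.
- A reader might infer that the scan is a commitment and that its best cut will be singled out. Item (c) is an example, PPV and NPV are listed for every candidate cut, and no readable text says one cut is chosen.
- A reader might infer that no correction exists anywhere. The redacted parts of SAP 11.4 are where cut-point methods would sit, so absence can be asserted only for the readable text, with the general no-adjustment rule in SAP 11.1 as the best evidence.

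The plan also has some safeguards: the preference for 10 or more per subgroup, a caution about robustness in small subgroups, and the covariate models in SAP 11.4.3. None of these corrects for choosing the cut.

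**Conclusion.** The point holds in a conditional form. If the scan in item (c) is run as the readable text describes, its per-cut p-values mislead even as descriptive measures. Any PPV or NPV quoted at a cut picked from the data will be too favourable. Under no association, about 23% of trials show at least one cut at p ≤ 0.05, against 3% for the median split. The range is 16% to 26% across minimum subgroup sizes, and 18% if a third of values tie at the bottom. These figures rest on a one-sided Fisher test at every cut, 100 evaluable subjects and a 26.4% ORR, for one biomarker and one endpoint. Looking at DRR, DOR or further biomarkers as well would raise the chance of some nominally significant cut.

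This is an improvement that should be made, not a breach of a stated error rate. It is subject to the sponsor confirming what the redacted parts of SAP 11.4 contain.

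**What to change.** 1. In the SAP, label the median-split Fisher test already planned in Protocol 10.2 as the lead analysis of the primary endpoint, and the other functional forms as supportive.
2. If the scan is run, fix its minimum subgroup size in advance. Report one permutation p-value for the maximally selected statistic, alongside or instead of the per-cut p-values: permute response across subjects, repeat the whole scan each time, and compare the observed smallest p with that distribution. Permutation also handles ties.
3. If any data-selected cut-off is reported, give its PPV and NPV with a bootstrap optimism correction that repeats the cut selection in every resample, and state that the cut was chosen on the same subjects.
4. If the redacted part of SAP 11.4 already does this, the sponsor need only confirm it and align SAP 11.1.

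The cost is a few lines of SAP text and a short program on data already being collected, with no new subjects, samples or visits. The downside is that the reported cut-point p-values, PPV and NPV become less favourable.

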10.4.3 Safety Endpoints

Subject incidence rates of treatment-emergent adverse events (including all adverse events, grade ≥ 3 adverse events, serious adverse events, adverse events of interest and events requiring the discontinuation of study drug, and local effects on the tumor [ie, pain, inflammation and ulceration]) will be summarized. Medical Dictionary for Regulatory Activities (MedDRA) will be used to code adverse events to a system organ class (SOC) and a preferred term within the SOC. The CTCAE version 3.0 will be used to grade severity of adverse events. In addition clinically significant laboratory changes

and clinically significant changes in vital signs will be summarized with descriptive statistics. Summary statistics will also be provided for concomitant medications, dose delay, study drug discontinuation, overall exposure, and changes in ECOG performance status. Tables and/or narratives of deaths after initiation of the study through 30 days since the last dose of talimogene laherparepvec will be provided.

The qPCR analysis result of talimogene laherparepvec DNA in swab samples taken from cold sore, vesicles, and other lesions suspected to be herpetic in origin (if any) will be summarized descriptively.

Potential or known unintended exposure to talimogene laherparepvec, related suspected signs or symptoms, and detection of talimogene laherparepvec in a subject's household member, caregiver, or healthcare provider will be reported.

10.4.4 Exploratory Endpoints

Correlation between the changes in the population of tumor specific cytotoxic T-cells and immunoscore during treatment and clinical response will be assessed by the same methods described in [Section 10.4](#). In addition, other potential blood and tumor biomarkers which predict ORR will be explored similarly.

10.5 Handling of Missing and Incomplete Data

Partial or missing dates of adverse events and concomitant medications will be imputed. Adverse events with missing severity and/or possible relationship to talimogene laherparepvec will be included in the all adverse events analyses, except by severity grade and treatment-related. Every effort will be made to obtain complete dates for deaths. Details of the imputation algorithms will be specified in the study-specific statistical analysis plan.

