3. EXPERIMENTAL PLAN

3.1 Study Design

This is a phase 2, multicenter, open-label, single-arm study to evaluate biomarkers in subjects with unresected stage IIIB to IVM1c melanoma who are treated with talimogene

laherparepvec. Subjects with unresected stage IIIB to IVM1c melanoma who meet the eligibility criteria outlined in [Section 4](#) will be considered for participation in this study.

Talimogene laherparepvec will be administered by intralesional injection into injectable cutaneous, subcutaneous, and nodal tumors initially at a dose of 10^6 Plaque-Forming Unit (PFU)/mL at study day 1 followed by a dose of 10^8 PFU/mL 21 (+5) days after the initial dose and every 14 (\pm 3) days thereafter. Subjects will be treated with talimogene laherparepvec until the subject has achieved a CR, all injectable tumors have disappeared, clinically significant (resulting in clinical deterioration or requiring change of therapy) disease progression beyond 6 months of treatment, per modified World Health Organization (WHO) response criteria ([WHO handbook for reporting results of cancer treatment, 1979](#); refer to [Appendix D](#)), or intolerance of study treatment, whichever occurs first. Due to the mechanism of action, subjects may experience **transient** growth of existing tumors or the appearance of new tumors prior to **achieving** maximal clinical benefit of talimogene laherparepvec. Therefore, dosing should be continued for at least 6 months from the time of initial dose regardless of progression provided that the subject is able to tolerate the treatment and does not develop deterioration of health status requiring other treatment.

Subjects will be followed for safety 30 (+ 7) days after the last dose of talimogene laherparepvec for survival, **adverse events thought by the investigator to be potentially related to talimogene laherparepvec, and use of anticancer therapies for melanoma** every 12 weeks (\pm 28 days) for up to approximately 24 months after the last subject is enrolled **in the study**. Thereafter, subjects will be followed under an ongoing separate registry protocol (Study 20120139) for the long-term survival follow-up of subjects treated with talimogene laherparepvec. The registry protocol will also monitor for late and long-term adverse events thought **by the investigator** to be potentially related to talimogene laherparepvec **and use of anti-cancer therapies for melanoma**.

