3.3 Number of Subjects

Participants in this clinical investigation shall be referred to as “subjects”. Approximately 110 subjects will be enrolled in the study. Refer to [Section 10.2](#) for sample size considerations.

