9.2 Reporting of Adverse Events

9.2.1 Reporting Procedures for Adverse Events That do not Meet Serious Criteria

The investigator is responsible for ensuring that all adverse events observed by the investigator or reported by the subject that occur after the first dose of talimogene laherparepvec through 30 (+ 7) days after the last dose of talimogene laherparepvec are reported using the applicable eCRF (eg, Adverse Event Summary). **Adverse events deemed by the investigator to be potentially related to talimogene laherparepvec that occur during and after the first dose of talimogene laherparepvec and through the survival follow-up are to be reported.**

The investigator must assign the following adverse event attributes:

- adverse event diagnosis or syndrome(s), if known (if not known, signs or symptoms),
- dates of onset and resolution (if resolved),
- severity (and/or toxicity per protocol),
- assessment of relatedness to talimogene laherparepvec and
- action taken.

The adverse event grading scale used will be the Common Terminology Criteria for Adverse Events (CTCAE), version 3.0. The grading scale used in this study is described in [Appendix A](#). The investigator must assess whether the adverse event is possibly related to talimogene laherparepvec. This relationship is indicated by a “yes” or “no” response to the question: Is there a reasonable possibility that the event may have been caused by administration of investigational product?

The investigator must assess whether the adverse event is possibly related to any study-mandated activity and/or procedure (eg, including any screening procedures). This relationship is indicated by a “yes” or “no” response to the question: “Is there a reasonable possibility that the event may have been caused by a study activity and/or procedure”?

The investigator is responsible for reviewing laboratory test results and determining whether an abnormal value in an individual study subject represents a clinically significant change from the subject’s baseline values. In general, abnormal laboratory findings without clinical significance (based on the investigator’s judgment) are not to be recorded as adverse events. However, laboratory value changes that require treatment

or adjustment in current therapy are considered adverse events. Where applicable, clinical sequelae (not the laboratory abnormality) are to be recorded as the adverse event.

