10.1.2 Analysis Sets

Safety Analysis Set: The safety analysis set will include all subjects who have received at least 1 dose of talimogene laherparepvec. The efficacy analysis and safety analysis will be performed on the safety analysis set.

Baseline Biomarker Analysis Set: The baseline biomarker analysis set will be defined separately for each baseline biomarker. The baseline biomarker analysis set includes all subjects who received at least 1 dose of talimogene laherparepvec and have the biomarker recorded at baseline. The correlation between a baseline biomarker and objective response rate, durable response rate, and duration of response will be conducted on the baseline biomarker analysis set.

Biomarker Evaluable Analysis Set: The biomarker evaluable analysis set will be defined separately for each biomarker. Lesions will be analyzed by injection status. The biomarker evaluable analysis set includes all subjects who received at least 1 dose of talimogene laherparepvec and have the biomarker recorded both at baseline and week 6. The correlation between biomarker changes during treatment and objective response rate, durable response rate, and duration of response will be conducted on the biomarker evaluable analysis set.

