10.3 Handling of Missing and Incomplete Data

Adverse events with missing severity, seriousness, and/or possible relationship to talimogene laherparepvec should not be imputed for study analyses. Missing data should be queried and resolved. **CCI** [REDACTED]

CCI

Partial or missing dates of adverse events and concomitant medications will be imputed.

CCI

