11.7 Analysis of Adverse Events

The Medical Dictionary for Regulatory Activities (MedDRA) version 16.1 or later will be used to code AEs to a system organ class (SOC) and a preferred term (PT) within the SOC. The CTCAE version 3.0 will be used to grade severity of AEs.

A table will be provided with a high-level summary of the subject incidence of any treatment-emergent adverse event and any treatment-emergent, treatment-related adverse event within the following categories: grade 3, grade 4, grades 3 or 4, fatal adverse events; serious; and leading to permanent discontinuation of protocol drug.

Additional subject incidence tables will be presented to describe the treatment-emergent and treatment-related adverse events (including all adverse events, grade ≥ 3 adverse events, serious adverse events, fatal adverse events, adverse events of interest, adverse events requiring permanent discontinuation of protocol drug, and local effects on the tumor[ie, pain, inflammation and ulceration]). Summaries of treatment-emergent and serious AEs occurring in at least 1% of the subjects by preferred term will be provided in descending order of frequency. The subject incidence summaries will be provided in 2 ways: within SOC subset by preferred term, and by decreasing order of preferred term frequency. In addition, adverse events and treatment-related adverse events will be tabulated by worst grade within SOC subset by preferred term.

Exposure-adjusted subject incidence and exposure-adjusted event rates may be estimated for specific AEs.

Listings will be provided for treatment-emergent and treatment-emergent, treatment-related adverse events (including all adverse events, serious adverse events, fatal adverse events, and adverse events requiring permanent discontinuation of protocol drug). In addition, screening SAEs prior to study Day 1 and all AEs > 30 days from last dose of study drug will be listed.

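### Adverse events whose relatedness stays missing are left out of the treatment-related tables, so treatment-related incidence is either unchanged or too low, never too high

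*Protocol*

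**What the plan says.** Protocol 10.5 states that adverse events lacking a severity grade or a relatedness value "will be included in the all adverse events analyses, except by severity grade and treatment-related". SAP 10.3 points the same way: "Adverse events with missing severity, seriousness, and/or possible relationship to talimogene laherparepvec should not be imputed for study analyses". It then adds "Missing data should be queried and resolved". The text directly after that is redacted.

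Relatedness is meant to be collected for every event. Protocol 9.2.1 says "The investigator must assess whether the adverse event is possibly related to talimogene laherparepvec", as a yes/no answer, and Protocol 9.2.2 asks the same for serious events.

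The summaries affected are described in SAP 11.7: "Additional subject incidence tables will be presented to describe the treatment-emergent and treatment-related adverse events". They cover all, grade 3 or higher, serious and fatal events, events of interest, and events leading to discontinuation. Protocol 10.1.1.2 lists these incidences as secondary safety endpoints. The denominator comes from Protocol 10.1.2: "The safety analysis set will include all subjects who have received at least 1 dose of talimogene laherparepvec". Nothing visible reduces that denominator when relatedness is missing, counts such events as related, reports how many there are, or plans a sensitivity table.

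**The concern.** Dropping an event from the numerator while its subject stays in the denominator is not neutral. Arithmetically it is the same as coding the event 'not related'. The rule reads as declining to impute, but in these tables it acts as imputation in the less cautious direction.

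The endpoint is a named one, and Protocol 3.1 describes an open-label, single-arm study, so no control arm carries the same omission. A reader of the treatment-related table would not know that its figure is a lower bound.

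The SAP also leans the other way on dates. In Appendix A, a missing start date is set to the date of first dose when the stop date is on or after first dose, or is also missing. The event then counts as treatment-emergent. Uncertain timing is resolved toward counting an event and uncertain causality toward not counting it, with no visible reason for the difference.

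**Working it through.** The plan gives no figure on this point, so there is nothing to reproduce. The check concerns the direction of the error and its size per subject.

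**Inputs**
- Rule: excluded from treatment-related summaries (Protocol 10.5); not imputed (SAP 10.3).
- Denominator: all treated subjects (Protocol 10.1.2; SAP Section 7).
- Planned size: "Approximately 110 subjects will be enrolled in the study" (Protocol 3.3). I assume all are treated, so N = 110.
- Number of unresolved records: not given.

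**Direction.** For one row of a treatment-related table, let R be the subjects with at least one event recorded as related. Let k be the subjects with none recorded as related but at least one with relatedness missing. Let T be the subjects who would count had every relatedness value been recorded. Some, all or none of the k subjects belong in T, so

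R/N ≤ T/N ≤ (R + k)/N.

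The planned figure is the left-hand side and counting missing as related gives the right-hand side. The planned figure equals T/N when the missing values would have been 'not related'. A subject who already counts in the row through another event is not among the k and changes nothing.

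A simulation of 2000 trials agrees. It used N = 110, about 5 events per subject, relatedness probability 5–95% and missingness 0–30%; these settings are assumptions made to test direction, not estimates for this trial.
- Exclusion gave a figure above the truth in 0 of 2000 trials, for subject incidence and for both exposure-adjusted measures defined in SAP Section 6.
- For subject incidence it equalled the truth in 404 trials and was lower in 2000 − 404 = 1596.
- Counting missing as related fell below the truth in 0 of 2000.

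One qualification: in a worst-grade tabulation, leaving out a subject's highest-grade event can move that subject into a lower-grade cell, so that single cell can rise. Overall severity is still understated.

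**Size.** The gap between the two bounds is k/N.

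| k | k/110 |
|---|---|
| 1 | 0.9 points |
| 3 | 2.7 points |
| 5 | 4.5 points |
| 10 | 9.1 points |

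Two illustrations, with k and the incidence assumed and exact 95% intervals:
- Common row: 55/110 = 50.0% (40.3–59.7%). With k = 3, 58/110 = 52.7% (43.0–62.3%). With k = 5, 60/110 = 54.5% (44.8–64.1%). The shift is small against the width of the interval.
- Rare row, such as treatment-related fatal events: 0/110 has an upper limit of 3.3%, while 1/110 = 0.9% (0.02–5.0%). Here one unresolved record decides whether the table shows a zero.

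**The case against.** The best defence is that the problem is prevented at source. Relatedness is a forced yes/no judgement, serious events reach the sponsor within 24 hours with a causality assessment (Protocol 9.2.2), data management checks for omissions and raises queries (Protocol 12.3), and SAP 10.3 asks for missing values to be resolved. The events are not lost either: they stay in the all-adverse-event tables and in the treatment-emergent listings, and deaths through 30 days after the last dose get tables or narratives (Protocol 10.4.3). The analyses are descriptive, the protocol and SAP agree with each other, and redacted SAP text may already cover residual cases. All of this stands, and it makes the point small. It does not change the direction, because a missing-data rule governs exactly what queries leave behind.

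A second objection is that counting missing as related exchanges a possible undercount for a possible overcount; one unresolved death from progression could appear as a treatment-related death. That is fair, and it is why both figures should be shown. It is also fair that missing severity pushes the grade 3 or higher rows the same way. This point is limited to relatedness, and severity would need its own rule.

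A reader might infer that the blanks will cluster in events followed by death or loss to follow-up, and so be mostly serious. The documents do not support that. Relatedness is the investigator's judgement and does not need the subject to be available, and serious events have the tightest reporting rules. A reader might also infer that the rule always understates. It does not: the figure is often simply unchanged.

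**Conclusion.** The point holds as a minor one. Any relatedness value still missing after query is in effect analysed as 'not related', so treatment-related subject incidence is unchanged or too low, and never too high. The size is 0.9 percentage points per affected subject, assuming all 110 planned subjects are treated. The number affected is unknown and probably very small, since the item is mandatory and queried. Only attribution to treatment is affected, not the overall count of adverse events. The conclusion rests on the visible text; the redacted part of SAP 10.3 could contain a further provision, and its absence from view is not a fault of the plan.

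**What to change.** In Protocol 10.5 and SAP 10.3, state that treatment-emergent adverse events, as defined in SAP Section 6, whose relatedness is still missing after query will be counted as treatment-related. Using that definition keeps out same-day events flagged as occurring before the first dose. Footnote the number of such events in the treatment-related tables, list them, and show the incidence with and without them so that both bounds are visible.

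The cost is a sentence or two in each document, plus a footnote, a listing and the second set of figures. The downside is that treatment-related incidence may be slightly overstated. If no unresolved records remain at database lock, no result changes.
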